#### **5.4.2. Mixed Model for Repeated Measures**

For the continuous secondary and exploratory efficacy and health outcome variables, such as EASI score and SCORAD score, MMRM analyses will be performed to mitigate the impact of missing data. This approach assumes that missing observations are missing-at-random (missingness is related to observed data) during the study and takes into account both the missingness of data and the correlation of the repeated measurements.

All continuous endpoints will utilize MMRM to patients who permanently discontinued study drug or who were rescued.

### **5.5. Multicenter Studies**

This study will be conducted by multiple investigators at multiple sites internationally. The countries will be categorized into geographic regions, as described in Section 4.2.

For the analysis of the primary endpoint, treatment-by-region interaction will be added to the logistic regression model as a sensitivity analysis and results from this model will be compared to the primary model (without the interaction effect). If the treatment-by-region interaction is significant at a 2-sided  $\alpha$  level of 0.1, the nature of this interaction will be inspected as to whether it is quantitative (ie, the treatment effect is consistent in direction across all regions but not in size of treatment effect) or qualitative (the treatment is beneficial in some but not all regions). If the treatment-by-region interaction effect is found to be quantitative, results from the primary model will be presented. If the treatment-by-region interaction effect is found to be qualitative, further inspection will be used to identify in which regions LY3375880 is found to be more beneficial.

### **5.6. Multiple Comparisons/Multiplicity**

No adjustments for multiplicity will be made for any analyses in this study.

### **5.7. Patient Disposition**

An overview of patient populations will be summarized by treatment group. Frequency counts and percentages of patients excluded prior to randomization by primary reason for exclusion will be provided for patients who failed to meet study entry requirements during screening.

Patient disposition through Week 16 will be summarized using the ITT population. Frequency counts and percentages of patients who complete the Induction Period and Maintenance Period or discontinue early from the study will be summarized separately by treatment group for patients who are not rescued and for patients who are rescued, along with their reason for study discontinuation. Frequency counts and percentages of patients who complete treatment or discontinue treatment early will also be summarized separately by treatment group for patients who are not rescued and for patients who are rescued, along with their reason for treatment discontinuation.

A listing of patient disposition will be provided for all randomized patients, with the extent of their participation in the study and the reason for discontinuation. A listing of all randomized patients with their treatment assignment will also be provided.

## 5.8. Patient Characteristics

Patient characteristics including demographics and baseline characteristics will be summarized descriptively by treatment group for the ITT population. Historical illnesses and pre-existing conditions will be summarized descriptively by treatment group for the ITT population.

Descriptive statistics including number of patients (n), mean, SD, minimum, median, and maximum will be provided for continuous measures, and frequency counts and percentages will be tabulated for categorical measures. No formal statistical comparisons will be made among treatment groups unless otherwise stated.

### 5.8.1. Demographics

Patient demographics will be summarized as described above. The following demographic information will be included:

- Age
- Age group (<65 vs.  $\geq 65$ )
- Age group (<65,  $\geq 65$  to <75,  $\geq 75$  to <85,  $\geq 85$ )
- Gender (male, female)
- Race (American Indian or Alaska Native, Asian, Black or African American, Native Hawaiian or Other Pacific Islander, White, Multiple)
- Region (Japan, Rest of World)
- Country
- Weight (kg)
- Height (cm)
- Body mass index ( $\text{kg}/\text{m}^2$ )

A listing of patient demographics will also be provided for the ITT population.

### 5.8.2. Baseline Disease Characteristics

The following baseline disease information (but not limited to only these) will be categorized and presented for baseline AD clinical characteristics, baseline health outcome measures, and other baseline demographic and disease characteristics as described above:

- Duration since AD diagnosis (years)
- Duration since AD diagnosis category (0 to <2 years, 2 to <5 years, 5 to <10 years, 10 to <20 years,  $\geq 20$  years)
- Validated Investigator's Global Assessment for AD (IGA) score
- Eczema Area and Severity Index (EASI) score
- SCORing Atopic Dermatitis (SCORAD)
- Body Surface Area (BSA) affected by AD
- Patient-Oriented Eczema Measure (POEM)
- Itch Numerical Rating Scale (NRS)

- Dermatology Life Quality Index (DLQI)
- Skin Pain NRS
- Immunoglobulin E (IgE): intrinsic(<200 kU/I) or extrinsic ( $\geq 200$  kU/I)

### **5.8.3. Historical Illness and Pre-existing Conditions**

Pre-existing Conditions and Medical History will be coded by Medical Dictionary for Regulatory Activities (MedDRA, most current available version). Data will be listed and summarized by treatment, system organ class (SOC), and preferred term (PT).

Pre-existing condition is defined as a condition with a start date on or before the informed consent date. Pre-existing conditions will be used to derive treatment-emergent adverse events (TEAEs).

## **5.9. Treatment Compliance**

In the Induction Phase, patient compliance with study medication will be assessed from Week 0 (Visit 2) to Week 16 (Visit 8) or Early Termination using the ITT population. In the Maintenance Phase, patient compliance with study medication will be assessed from Week 16 (Visit 8) to Week 52 (visit 17) or Early Termination using the Maintenance Period population.

All doses of study medication will be administered at the study site by study personnel. Patients who miss 20% of the expected doses through Week 16(Visit 8, exclusive) or through Week 52 (Visit 17) will be excluded from the PPS population in the Induction Period and Maintenance Period, respectively.

Descriptive statistics for percent compliance and non-compliance rate will be summarized for the ITT population by treatment group for Week 0 through Week 16, and for the Maintenance Period population by treatment group for Week 16 through Week 52, with data up to rescue. .Percent compliance will be listed by patient for Week 0 through Week 16 and for Week 16 through Week 52, with data up to rescue.

### **5.9.1. Rescue Treatment**

Summaries of patients receiving rescue therapy at each visit will be provided.

## **5.10. Previous and Concomitant Therapy**

Summaries of previous and concomitant medications will be based on the ITT population.

Concomitant therapy for the treatment period is defined as therapy that starts before or during the treatment period and ends during the treatment period or is ongoing (has no end date or ends after the treatment period). Should there be insufficient data to make this comparison (for example, the concomitant therapy stop year is the same as the treatment start year, but the concomitant therapy stop month and day are missing), the medication will be considered as concomitant for the treatment period.

## 5.11. Efficacy and Health Outcome Analyses

The general methods used to summarize efficacy data, including the definition of baseline value for assessments are described in Section 5.1.

Table FCAB.5.1 includes the descriptions and derivations of the primary, secondary, and exploratory efficacy and health outcomes.

Table FCAB.5.2 provides the detailed analyses including analysis type, method and imputation, population, time point, and comparisons for efficacy and health outcome analyses.

**Table FCAB.5.1. Description and Derivation of Primary, Secondary and Exploratory Efficacy Outcomes**

| Measure   | Description   | Variable  | Derivation / Comment  | Imputation Approach if with Missing Components   |
|---|---|---|---|--|
| Validated Investigator's Global Assessment for AD (IGA) | The validated Investigator's global assessment of the patient's overall severity of their AD, based on a static, numeric 5-point scale from 0 (clear) to 4 (severe). The score is based on an overall assessment of the degree of erythema, papulation/induration, oozing/crusting, and lichenification.  | 
 
▪ IGA score
 
▪ Change from baseline in IGA score
 
▪ IGA [0,1] with <math>\geq 2</math>-point improvement
 
▪ IGA [0]
 
 | 
Single item. Range: 0 to 4
0 represents "clear"
4 represents "severe"
 
Change from baseline: observed IGA score – baseline IGA score
 
 
▪ Observed score of 0 or 1 and change from baseline <math>\leq -2</math>
 
▪ Observed score of 0
 
   | 
Single item, missing if missing.
 
Missing if baseline or observed value is missing.
 
 
▪ Missing if baseline or observed value is missing.
 
▪ Single item, missing if missing.
 
 |
| Eczema Area and Severity Index (EASI)                   | The EASI assesses objective physician estimates of 2 dimensions of atopic dermatitis – disease extent and clinical signs (Hanifin et al 2001) – by scoring the extent of disease (percentage of skin affected: 0 = 0%; 1 = 1-9%; 2 = 10-29%; 3 = 30-49%; 4 = 50-69%; 5 = 70-89%; 6 = 90-100%) and the severity of 4 clinical signs (erythema, edema/papulation, excoriation, and lichenification) each on a scale of 0 to 3 (0 = none, absent; 1 = mild; 2 = moderate; 3 = severe) at 4 body sites (head and neck, trunk, upper limbs, and lower limbs). Half scores are allowed. Each body site will have a score that ranges from 0 to 72, and the final EASI score will be obtained by weight-averaging these 4 scores. Hence, the final EASI score will range from 0 to 72 for each time point. | 
 
▪ EASI score
 
  | 
Derive EASI region score for each of head and neck, trunk, upper limbs, and lower limbs as follows:
 <math>EASI_{region} = (Erythema + edema/papulation + Excoriation + Lichenification) * (value from percentage involvement)</math>, where erythema, edema/papulation, excoriation, and lichenification are evaluated on a scale of 0 to 3 and value from percentage involvement is on a scale of 0 to 6.
 
Then total EASI score is as follows:
 <math>EASI = 0.1 * EASI_{head and neck} + 0.3 * EASI_{trunk} + 0.2 * EASI_{upper limbs} + 0.4 * EASI_{lower limbs}</math>
 | N/A – partial assessments cannot be saved.   |
|   |   | 
 
▪ Change from baseline in EASI score
 
▪ Percent change from baseline EASI score
 
   | 
Change from baseline: observed EASI score – baseline EASI score
 
% change from baseline:
 <math display="block">100 \times \frac{Observed score - Baseline}{Baseline}</math>
   | Missing if baseline or observed value is missing.  |
|   |   | ▪ EASI75  | % Improvement in baseline $\geq 75\%$ or % change from baseline $\leq -75\%$  | Missing if baseline or observed value is missing.  |

| Measure                                | Description  | Variable   | Derivation / Comment   | Imputation Approach if with Missing Components  |
|--|--|--|--|---|
|  |  | 
 
EASI90
 
   | % Improvement in baseline $\geq 90\%$ or
% change from baseline $\leq -90\%$  | Missing if baseline or observed value is missing.   |
| Body Surface Area (BSA) Affected by AD | Body surface area affected by AD will be assessed for 4 separate body regions and is collected as part of the EASI assessment: head and neck, trunk (including genital region), upper extremities, and lower extremities (including the buttocks). Each body region will be assessed for disease extent ranging from 0% to 100% involvement. The overall total percentage will be reported based off of all 4 body regions combined, after applying specific multipliers to the different body regions to account for the percent of the total BSA represented by each of the 4 regions. | 
 
BSA score
 
  | Use the percentage of skin affected for each region (0 to 100%) in EASI as follows:
$\text{BSA} = \text{BSA}_{\text{head and neck}}/100/0.10 + \text{BSA}_{\text{trunk}}/100/0.0333 + \text{BSA}_{\text{upper limbs}}/100/0.05 + \text{BSA}_{\text{lower limbs}}/100/0.025$ | N/A – partial assessments cannot be saved.  |
| SCORing Atopic Dermatitis (SCORAD)     |  | 
 
SCORAD score
 
   | $\text{SCORAD} = A/5 + 7B/2 + C$ , where
A is extent of disease, range 0-100
B is disease severity, range 0-18
C is subjective symptoms, range 0-20   | Missing if components A and B are missing or if component C is missing.
Partial assessments performed by physician cannot be saved and partial assessments performed by patient cannot be saved. |
|  |  | 
 
Change from baseline in SCORAD score
 
Percent change from baseline in SCORAD score
 
 | Change from baseline: observed SCORAD score – baseline SCORAD score
% change from baseline:
$100 \times \frac{\text{Observed score} - \text{Baseline}}{\text{Baseline}}$   | Missing if baseline or observed value is missing.   |

| Measure | Description  | Variable   | Derivation / Comment  | Imputation Approach if with Missing Components  |
|---------|--|--|---|---|
|         | 
The SCORing Atopic Dermatitis (SCORAD) index uses the rule of nines to assess disease extent (head and neck 9%; upper limbs 9% each; lower limbs 18% each; anterior trunk 18%; back 18%; and genitals 1%). It evaluates 6 clinical characteristics to determine disease severity: (1) erythema, (2) edema/papulation, (3) oozing/crusts, (4) excoriation, (5) lichenification, and (6) dryness on a scale of 0 to 3 (0=absence, 1=mild, 2=moderate, 3=severe). The SCORAD index also assesses subjective symptoms of pruritus and sleep loss in the last 72 hours on visual analogue scales (VAS) of 0 to 10 where 0 is no itch or sleep loss and 10 is worst imaginable itch or sleep loss. These 3 aspects: extent of disease, disease severity, and subjective symptoms combine to give a maximum possible score of 103 (Stalder et al. 1993; Kunz et al. 1997; Schram et al. 2012).
 | 
 
▪ SCORAD75
 
▪ SCORAD90
 
 | 
% Improvement in baseline <math>\geq 75\%</math>:
 % change from baseline <math>\leq 75</math>
 
% Improvement in baseline <math>\geq 90\%</math>:
 % change from baseline <math>\leq 90</math>
 | 
Missing if baseline or observed value is missing.
 
Missing if baseline or observed value is missing.
 |

| Measure                              | Description   | Variable                                | Derivation / Comment   | Imputation Approach if with Missing Components   |
|--------------------------------------|---|---|--|--|
| Itch Numeric Rating Scale (NRS)      | The Itch Numeric Rating Scale (NRS) is a patient-administered, 11-point horizontal scale anchored at 0 and 10, with 0 representing “no itch” and 10 representing “worst itch imaginable.” Overall severity of a patient’s itching is indicated by selecting the number that best describes the worst level of itching in the past 24 hours (Naegeli et al. 2015; Kimball et al. 2016). Refer to Section 5.2.2 for details on how to calculate the weekly score which will be used in the continuous analysis. | ▪ Itch NRS score                        | Single item; range 0-10. Refer to Section 5.2.2 on how to derive the visit score.    | Refer to Section 5.2.2 on how to derive the visit score.   |
|                                      |   | ▪ Change from baseline in Itch NRS      | Change from baseline: observed Itch NRS score – baseline Itch NRS score              | Missing if baseline or observed value is missing. Refer to Section 5.2.2 on how to derive the visit score. |
| Skin Pain Numeric Rating Scale (NRS) | Skin Pain NRS is a patient-administered, 11-point horizontal scale anchored at 0 and 10, with 0 representing “no pain” and 10 representing “worst pain imaginable.” Overall severity of a patient’s skin pain is indicated by selecting the number that best describes the worst level of skin pain in the past 24 hours. Refer to Section 5.2.2 for details on how to calculate the weekly score which will be used in the continuous analysis.  | ▪ Skin Pain NRS score                   | Single item; range 0 to 10. Refer to Section 5.2.2 on how to derive the visit score. | Refer to Section 5.2.2 on how to derive the visit score.   |
|                                      |   | ▪ Change from baseline in Skin Pain NRS | Change from baseline: observed skin pain score – baseline skin pain score            | Missing if baseline or observed value is missing.  |

| Measure                                 | Description | Variable   | Derivation / Comment   | Imputation Approach if with Missing Components  |
|---|-------------|--|--|---|
|   |             | 
 
▪ Frequency of No Pain (Skin pain NRS = 0)
 
 | 
Count of observed value = 0 starting on the day of the previous study visit to the day prior to the subsequent study visit. This only applies to scheduled study visits and thus will be calculated for the following visit intervals: Week 0 to Week 1, Week 1 to Week 2, Week 2 to Week 4, Week 4 to Week 8, Week 8 to Week 12 and Week 12 to Week 16. The number of observations with value = 0 will then be pro-rated for the interval; intervals of 1 week will be adjusted to 7 days, 2 weeks to 14 days and 4 weeks to 28 days. For example, if the patient has 5 assessments with a value of 0 from Week 12 to Week 16 with 30 of the 35 days occurring between the visits having non-missing values, the pro-rated count will be <math>5/30*28=4.7</math>.
 | 
If patients do not have at least an average of 4 values for each week in the visit interval (eg, at least 4 non-missing assessments for Week 1 to Week 2, at least 8 non-missing assessments from Week 2 to Week 4, at least 16 non-missing assessments from Week 12 to 16), the score is missing.
 |
| Patient- Oriented Eczema Measure (POEM) |             | 
 
▪ POEM score
 
                               | 
POEM total score: sum of questions 1 to 7, Range 0 to 28.
   | 
If a single question is left unanswered, then that question is scored as 0. If more than one question is unanswered, then the tool is not scored. If more than one response is selected, then the response with the highest score is used.
   |

| Measure                               | Description   | Variable   | Derivation / Comment   | Imputation Approach if with Missing Components           |
|---------------------------------------|---|--|--|--|
|                                       | 
The POEM is a simple, 7-item, patient-administered scale that assesses disease severity in children and adults. Patients respond to questions about the frequency of 7 symptoms (itching, sleep disturbance, bleeding, weeping/oozing, cracking, flaking, and dryness/roughness) over the last week. Response categories include “No days,” “1-2 days,” “3-4 days,” “5-6 days,” and “Every day” with corresponding scores of 0, 1, 2, 3, and 4, respectively. Scores range from 0-28 with higher total scores indicating greater disease severity (Charman et al. 2004).
 | 
 
▪ Change from baseline in POEM score
 
 | 
Change from baseline: observed POEM score – baseline POEM score
   | 
Missing if baseline or observed value is missing.
 |
| Dermatology Life Quality Index (DLQI) |   | 
 
▪ Symptoms and feelings domain
 
       | 
Sum of questions 1 and 2, range 0 to 6.
   | 
N/A – partial assessments cannot be saved.
        |
|                                       |   | 
 
▪ Daily activities domain
 
            | 
Sum of questions 3 and 4, range 0 to 6.
   | 
N/A – partial assessments cannot be saved.
        |
|                                       |   | 
 
▪ Leisure domain
 
                     | 
Sum of questions 5 and 6, range 0 to 6.
   | 
N/A – partial assessments cannot be saved.
        |
|                                       |   | 
 
▪ Work and school domain
 
             | 
Sum of questions 7 and 7B (if it is answered), range 0 to 3.
Responses of “yes” and “no” on Question 7 are given scores of 3 and 0 respectively. If Question 7 is answered “no” then Question 7b is answered with “a lot”, “a little”, “not at all” getting scores of 2, 1, 0 respectively.
 | 
N/A – partial assessments cannot be saved.
        |
|                                       |   | 
 
▪ Personal relationships domain
 
      | 
Sum of questions 8 and 9, range 0 to 6.
   | 
N/A – partial assessments cannot be saved.
        |
|                                       |   | 
 
▪ Treatment domain
 
                   | 
Question 10, range 0 to 3.
  | 
N/A – partial assessments cannot be saved.
        |

| Measure | Description  | Variable   | Derivation / Comment  | Imputation Approach if with Missing Components   |
|---------|--|--|---|--|
|         | 
The Dermatology Life Quality Index (DLQI) is a simple, patient-administered, 10-item, validated, quality-of-life questionnaire that covers 6 domains including symptoms and feelings, daily activities, leisure, work and school, personal relationships, and treatment. The recall period of this scale is over the “last week.” Response categories include “a little,” “a lot,” and “very much,” with corresponding scores of 1, 2, and 3, respectively, and “not at all,” or unanswered (“not relevant”) responses scored as 0. Scores range from 0-30 with higher scores indicating greater impairment of quality of life. A DLQI total score of 0 to 1 is considered as having no effect on a patient’s health-related QoL (Hongbo et al. 2005), and a 4-point change from baseline is considered as the minimal clinically important difference threshold (Khilji et al. 2002; Basra et al. 2015).
 | 
 
▪ DLQI total score
 
▪ Change from baseline in DLQI
 
 | 
DLQI total score: sum of all six DLQI domain scores, range 0 to 30.
 
Change from baseline: observed DLQI score – baseline DLQI score
 | 
N/A – partial assessments cannot be saved.
 
Missing if baseline or observed value is missing.
 |

Table FCAB.5.2. Description of Primary, Secondary and Exploratory Efficacy Analyses

| Measure   | Variable  | Analysis Method (Section 5.2.3) | Population (Section 5.2.1) | Comparison/Time Point   | Analysis Type        |
|---|---|---------------------------------|----------------------------|---|----------------------|
| Validated Investigator's Global Assessment for AD (IGA) | • Proportion of patients achieving IGA [0,1] with a $\geq 2$ -point improvement   | Logistic regression using NRI   | ITT; PPS                   | LY3375880 600-mg or LY3375880 150-mg or LY3375880 50-mg vs PBO; Week 16                     | Primary analysis     |
|   | • Proportion of patients achieving IGA [0]  |                                 | Maintenance                | LY3375880 600-mg or LY3375880 300-mg or LY3375880 150-mg or LY3375880 50-mg vs PBO; Week 52 | Secondary analysis   |
|   | • Proportion of patients achieving IGA [0]  | Logistic regression using NRI   | ITT                        | LY3375880 600-mg or LY3375880 150-mg or LY3375880 50-mg vs PBO; Week 16                     | Secondary analysis   |
| Eczema Area and Severity Index (EASI)                   | • EASI score
• Change from baseline in EASI score
• Percent change from baseline in EASI score                                | MMRM                            | ITT; PPS                   | LY3375880 600-mg or LY3375880 150-mg or LY3375880 50-mg vs PBO; Week 16                     | Secondary analysis   |
|   | • Proportion of patients achieving EASI50
• Proportion of patients achieving EASI75
• Proportion of patients achieving EASI90 | Logistic regression using NRI   | ITT; PPS                   | LY3375880 600-mg or LY3375880 150-mg or LY3375880 50-mg vs PBO; Week 16                     | Secondary analysis   |
| Body Surface Area (BSA) Affected by AD                  | • BSA score
• Change from baseline in BSA score  | MMRM                            | ITT                        | LY3375880 600-mg or LY3375880 150-mg or LY3375880 50-mg vs PBO; Week 16                     | Exploratory analysis |
| SCORing Atopic Dermatitis (SCORAD)                      | • SCORAD score
• Change from baseline in SCORAD score
• Percent change from baseline in SCORAD score                          | MMRM                            | ITT                        | LY3375880 600-mg or LY3375880 150-mg or LY3375880 50-mg vs PBO; Week 16                     | Secondary analysis   |
|   | • Proportion of patients achieving SCORAD75
• Proportion of patients achieving SCORAD90  | Logistic regression using NRI   | ITT; PPS                   | LY3375880 600-mg or LY3375880 150-mg or LY3375880 50-mg vs PBO; Week 16                     | Secondary analysis   |

| Measure                                | Variable   | Analysis Method (Section 5.2.3) | Population (Section 5.2.1)                              | Comparison/Time Point   | Analysis Type        |
|--|--|---------------------------------|---|---|----------------------|
| Itch NRS                               | • Itch NRS score
• Change from baseline in Itch NRS score             | MMRM                            | ITT; PPS  | LY3375880 600-mg or LY3375880 150-mg or LY3375880 50-mg vs PBO; Week 16 | Exploratory Analysis |
|  | • Proportion of patients with at least a 4-point improvement in Itch NRS | Logistic regression using NRI   | ITT; PPS (those with baseline Itch NRS of 4 or greater) | LY3375880 600-mg or LY3375880 150-mg or LY3375880 50-mg vs PBO; Week 16 | Exploratory Analysis |
| Skin Pain Numeric Rating Scale (NRS)   | • Skin Pain NRS score
• Change from baseline in Skin Pain NRS score   | MMRM                            | ITT; PPS  | LY3375880 600-mg or LY3375880 150-mg or LY3375880 50-mg vs PBO; Week 16 | Exploratory Analysis |
| Patient-Oriented Eczema Measure (POEM) | • POEM score
• Change from baseline in POEM score                     | MMRM                            | ITT   | LY3375880 600-mg or LY3375880 150-mg or LY3375880 50-mg vs PBO; Week 16 | Exploratory Analysis |
| Dermatology Life Quality Index (DLQI)  | • DLQI total score
• Change from baseline in DLQI                     | MMRM                            | ITT   | LY3375880 600-mg or LY3375880 150-mg or LY3375880 50-mg vs PBO; Week 16 | Exploratory Analysis |

Abbreviations: ITT = intent-to-treat; MMRM = mixed model repeated measures; NRI = nonresponder imputation; NRS = Numeric Rating Scale; PBO = placebo; PPS = per protocol set.

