10.2.3.2. Secondary Analyses

The previously described logistic regression model will be used to analyze the proportion of subjects achieving the following:

- IGA of 0 at Week 16
- EASI-50, EASI-75, and EASI-90 at Week 16, where EASI-75 and EASI-90 are defined as having an improvement of at least 75% and 90% from baseline, respectively.
- SCORAD75 and SCORAD90 at Week 16, where SCORAD75 and SCORAD90 are defined as having an improvement of at least 75% and 90% from baseline, respectively.
- IGA of 0 or 1 at Week 52

The previously described MMRM model will be used to analyze mean change from baseline for:

- EASI score
- SCORAD score

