#### **5.4.1. Nonresponder Imputation**

For the analysis of categorical efficacy and health outcomes variables such as IGA(0,1) and EASI50/75/90, the primary method to impute missing data will be a nonresponder imputation (NRI) method.

All categorical endpoints will utilize the NRI method to patients who permanently discontinued study drug or were rescued.

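### The SAP's percent-change cut-offs for SCORAD75 and SCORAD90 lack the minus sign and contradict the improvement rule in the same table cell

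*SAP*

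**What the plan says.** SAP Section 5.11 names Table FCAB.5.1 as the place where efficacy outcomes are described and derived. For SCORAD, the table takes change as observed minus baseline, and percent change as that difference divided by baseline, times 100. A higher SCORAD is worse, so improvement carries a negative sign.

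Each SCORAD responder cell holds two lines joined by a colon. For SCORAD75 the first line is "Improvement in baseline \geq 75" percent and the second, on the percent-change scale, is "change from baseline \leq 75". SCORAD90 follows the same pattern, with an improvement of at least 90% and then "change from baseline \leq 90".

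Three other places bear on the intended rule:

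- The EASI75 row of the same table gives both forms with the sign in place: "Improvement in baseline $\geq 75\%$ or % change from baseline $\leq -75" percent. The EASI90 row does likewise with −90%.
- The IGA row of the same table also keeps its sign: "Observed score of 0 or 1 and change from baseline \leq -2".
- Protocol 10.2.3.2 states that "SCORAD75 and SCORAD90 are defined as having an improvement of at least 75% and 90% from baseline, respectively".

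Table FCAB.5.2 lists SCORAD75 and SCORAD90 at Week 16 as secondary analyses, by logistic regression with NRI in the ITT and per-protocol populations.

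**The concern.** Under the SAP's own formula, the two lines in each SCORAD cell describe different sets of subjects. The improvement line selects those who lost at least 75% or 90% of their baseline score. The percent-change line selects everyone whose score did not rise by more than 75% or 90%.

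This table is the derivation specification for two secondary endpoints, and percent change in SCORAD is itself a listed variable, so the faulty line is easy to turn directly into code. The SAP does not say how the two lines combine. If both must be met, the endpoint is right. If the second is taken to put the first into operation, or if the lines are joined by the word that the EASI rows use (or), the rule collapses to the faulty line. The responder rate would then say little about skin improvement and would mostly reflect rescue, discontinuation and missing data, because "All categorical endpoints will utilize the NRI method to patients who permanently discontinued study drug or were rescued".

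**Working it through.** **Inputs** (SAP Table FCAB.5.1 unless stated)

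- Percent change: c = 100 × (observed − baseline)/baseline.
- SCORAD = A/5 + 7B/2 + C, with A up to 100, B up to 18 and C up to 20.
- Printed cut-offs: c ≤ 75 and c ≤ 90.
- Improvement cut-offs: at least 75% and at least 90%.
- Planned arm size: 50 (Protocol Section 10).

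**Step 1. Scale maximum.** 100/5 + 7 × 18/2 + 20 = 20 + 63 + 20 = 103, which reproduces the stated maximum.

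**Step 2. Equivalent cut-offs.** Percent improvement is −c. Improvement ≥ 75% is therefore c ≤ −75, and improvement ≥ 90% is c ≤ −90. The printed values differ from these by the sign.

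**Step 3. What each rule requires at Week 16.** Solving for the observed score, the intended rules are observed ≤ 0.25 × baseline (SCORAD75) and ≤ 0.10 × baseline (SCORAD90). The printed rules are observed ≤ 1.75 × baseline and ≤ 1.90 × baseline. The baselines below are chosen for illustration.

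| Baseline | Endpoint | Intended cut-off | Printed cut-off |
|---|---|---|---|
| 40 | SCORAD75 | 0.25 × 40 = 10 | 1.75 × 40 = 70 |
| 40 | SCORAD90 | 0.10 × 40 = 4 | 1.90 × 40 = 76 |
| 60 | SCORAD75 | 0.25 × 60 = 15 | 1.75 × 60 = 105 |
| 60 | SCORAD90 | 0.10 × 60 = 6 | 1.90 × 60 = 114 |

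At a baseline of 60 both printed cut-offs exceed 103. A subject who stays at 60 (c = 0) or worsens to 72 (c = +20) meets both printed rules and neither improvement rule.

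**Step 4. Baseline from which no score can fail.**

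- SCORAD75: 103/1.75 = 58.86, so 58.9 to one decimal. From 58.9 a rise to 103 is +74.87%; from 58.8 it is +75.17%.
- SCORAD90: 103/1.90 = 54.21, so 54.3 to one decimal. From 54.3 a rise to 103 is +89.69%; from 54.2 it is +90.04%.

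**Step 5. Nesting.** Correctly, every SCORAD90 responder is a SCORAD75 responder. Under the printed lines, c ≤ 75 implies c ≤ 90, so every SCORAD75 responder is a SCORAD90 responder. The stricter endpoint becomes the looser one.

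**Step 6. Effect on the ITT rate (assumption).** The documents give no rescue or dropout rate. Suppose that a share q of an arm of 50 is set to nonresponse by NRI and all others meet the printed line. The rate is then 1 − q: 45/50 = 90% at q = 0.10, and 25/50 = 50% at q = 0.50.

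**Step 7. Check of the correction.** With ≤ −75 and ≤ −90, the percent-change and improvement lines classified every test case identically, for baselines of 40 to 80 with scores capped at 103.

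**The case against.** The strongest reply has three parts.

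First, a minus sign can be lost when a PDF is converted to text, and the SCORAD lines also lack the percent sign that the EASI rows carry. That would fit a conversion fault as well as a drafting slip. This stands as a reason to look at the source PDF first. It does not make conversion loss likely: the IGA and EASI rows of the same table keep their signs, and the fault appears in both SCORAD lines.

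Second, the intended rule is not in doubt. The line above states it correctly, as does the protocol. A programmer would have to pass over both and code the second line alone, and the output would look odd, with unchanged subjects as responders and reversed nesting. This also stands, and it is why the harm is conditional. But the SAP does not say that both lines must hold, and the parallel EASI rows join theirs with an or, which here would give the wrong rule.

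Third, the illustrative baselines and NRI shares come from outside the documents. That is true. They show what the printed rule would do; they do not forecast this trial's results.

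**Conclusion.** The concern holds. As written, the percent-change lines for SCORAD75 and SCORAD90 have the wrong sign under the SAP's own formula. They contradict the same cells, the EASI rows and Protocol 10.2.3.2. It is a wrong threshold in the derivation table for two Week 16 secondary endpoints and should be fixed.

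The consequence depends on the faulty line being coded alone or joined to the first by or. In that case nearly all subjects not set to nonresponse would count as responders, and from the baselines in Step 4 upward all of them would. How many subjects that covers is unknown, because the documents give no baseline SCORAD distribution. If both lines are required together, the endpoints are correct. The primary endpoint, the sample size and the SCORAD mean-change analysis do not depend on these lines. The remaining uncertainty is whether the signs are absent from the source PDF too.

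**What to change.** Confirm the two lines against the source PDF. If the signs are missing there, change them in Table FCAB.5.1 to a percent change from baseline of ≤ −75% for SCORAD75 and ≤ −90% for SCORAD90. Each cell then agrees with its own improvement line, the EASI rows and the protocol. It is also worth asking the programmer to confirm that every SCORAD90 responder is a SCORAD75 responder, since the faulty rule reverses that order.

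The cost is a few characters in one SAP table. Design, data collection and sample size do not change.
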